5.2.4. Estimand for estimated GFR (eGFR) time trajectory

This is de-facto (effectiveness) estimand for eGFR trajectory with the following attributes:

A1. Target population: Individuals with T1D meeting the inclusion/exclusion criteria specified in the Study Protocol.

A2. Variable of interest (endpoint): Repeated eGFR measures at all post-randomization visits (Visit 6 through 17) as estimated from repeated serum creatinine and cystatin C measurements using the CKD-EPI SCr and the CKD-EPI SCr-SCysC equations.

A3. Strategies for different groups of IC events: The same as those used for primary estimand (see Section 5.1)

A4. Population summary to compare treatments: Population-average treatment effect on the slope of post-randomization eGFR trajectory

5.2.5. Estimand for time to doubling of serum creatinine or end-stage renal disease (ESRD)

This is de-facto (effectiveness) estimand for doubling of serum creatinine or developing ESRD with the following attributes.

A1. Target population: Individuals with T1D meeting the inclusion/exclusion criteria specified in the Study Protocol.

A2. Variable of interest (endpoint): This secondary endpoint is defined as a composite of two events: (1) doubling to serum creatinine, and (2) ESRD. Time to event is defined as time from randomization to the first event (one of the events defined above) or censoring (lost-to-follow-up, withdrawal, death, and study completion without experiencing the event).

A3. Strategies for different groups of IC events: Depending on IC event group membership (see Table 5.1) variable of interest/endpoint values, collected after IC event in

- Group A will be considered as directly interpretable. Effectively IC events in this group are ignored, which is consistent with the ITT principle.

- Groups B and C are assumed to conform a hypothetical scenario in which the variable of interest/endpoint values have a similar distribution to subjects not experiencing the IC event.

A4. Population summary to compare treatments: Hazard ratio for allopurinol versus placebo.

5.2.6. Estimand for urinary AER at the end of the two-month wash-out period (Visit 17)

This is de-facto (effectiveness) estimand for AER at V17 with the following attributes.

A1. Target population: Individuals with T1D meeting the inclusion/exclusion criteria specified in the Study Protocol.

A2. Variable of interest (endpoint): Geometric mean of two urinary AER measures obtained at Visit 17.

A3. Strategies for different groups of IC events: Depending on IC event group membership (see Table 5.1) variable of interest/endpoint values, collected after IC event in

- Group A will be considered as directly interpretable. Effectively IC events in this group are ignored, which is consistent with the ITT principle.

- Groups B and C are assumed to conform a hypothetical scenario in which the variable of interest/endpoint values have a similar distribution to subjects not experiencing the IC event.

A4. Population summary to compare treatments: Population-average treatment effect on AER at V17 expressed as a ratio of geometric means.

5.2.7. Estimand for urinary AER during the last three months of the treatment period (Visits 15 and 16)

This is de-facto (effectiveness) estimand for AER at Visit 15 and 16 with the following attributes:

A1. Target population: Individuals with T1D meeting the inclusion/exclusion criteria specified in the Study Protocol.

A2. Variable of interest (endpoint): Geometric mean of urinary AER measures at Visit 15 and Visit 16.

A3. Strategies for different groups of IC events: Depending on IC event group membership (see Table 5.1) variable of interest/endpoint values, collected after IC event in

- Group A will be considered as directly interpretable. Effectively IC events in this group are ignored, which is consistent with ITT principle.
- Groups B and C are assumed to conform a hypothetical scenario in which the variable of interest/endpoint values have a similar distribution to subjects not experiencing the IC event.

A4. Population summary to compare treatments: Population-average treatment effect on AER during last three months of the treatment expressed as a ratio of geometric means.

5.2.8. Estimand for the time to fatal or non-fatal cardiovascular events endpoint

This is de-facto (effectiveness) estimand for fatal and non-fatal cardio-vascular events with the following attributes:

A1. Target population: Individuals with T1D meeting the inclusion/exclusion criteria specified in the Study Protocol.

A2. Variable of interest (endpoint): This secondary endpoint is defined as a composite of multiple events: (1) Cardiovascular disease (CVD) death (ICD-10 code I10 to I74.9), (2) Myocardial infarction, (3) Stroke (ischemic or hemorrhagic), (4) Coronary artery bypass grafting, or (5) Percutaneous coronary intervention. Time to fatal or non-fatal cardiovascular events is defined as the time from randomization to the first event (one of the events defined above) or censoring (lost-to-follow-up, withdrawal, non-CVD death, and study completion without experiencing the event).

A3. Strategies for different groups of IC events: Depending on IC event group membership (see Table 5.1) variable of interest/endpoint values, collected after IC event in

- Group A will be considered as directly interpretable. Effectively IC events in this group are ignored, which is consistent with ITT principle.
- Groups B and C (except CVD death) are assumed to conform a hypothetical scenario in which variable of interest/endpoint values have similar distribution to subjects not experiencing IC event.

A4. Population summary to compare treatments: Hazard ratio for allopurinol versus placebo

6. Analytical Strategy

In the initial analysis of the primary outcome we will present iGFR univariate statistics by Treatment Groups at each study visit (V4, V11, V16 and V17).

No formal interim analyses of the primary endpoint will be conducted, therefore the nominal α level to be used at the final analysis will be 0.05 for the primary endpoint. All other secondary outcomes will also be tested at the 0.05 level, with no adjustment for multiplicity. Many of the models used in the analyses include baseline covariates, such as stratifying variables (serum uric acid (sUA), HbA1C, clinical site), iGFR, albuminuria status (subjects who qualified by ACR or AER or were albuminuric at baseline vs. subjects who qualified by eGFR slope and were normoalbuminuric at baseline), AER, and time, and time by treatment interaction. If there are problems with fitting these models, due, for example, to lack of convergence to optimal values, covariates will be eliminated from the models in the following order: baseline AER, albuminuria status, serum uric acid (sUA), HbA1c, and clinical site. More detailed information about these covariates is included in Section 6.4.

6.1. Study populations

Two study populations will be defined for the purpose of data analysis:

- **Intention to Treat (ITT):** The ITT analysis set consists of all subjects enrolled in PERL, randomized to study medication.
- **Per Protocol:** The per protocol analysis set will consist of a subset of ITT subjects. The per protocol population will exclude subjects with major protocol deviations (defined as receiving the wrong study medication) as well as subjects for whom the average drug exposure is less than 80% (see Section 11.1 in the protocol).

To account for missing values in any specific analysis, all subjects meeting the study population definitions will be included and analyzed using (1) multiple imputation techniques (see Section 6.4), or (2) appropriate analytical approaches that allow for missing values under plausible missing data mechanisms, such as linear mixed-effects models that allow values of the dependent variable to be missing under missing at random (MAR) mechanism.

Long study follow-up results in missing values for the outcomes and precludes strict adhering to ITT principle. To mitigate this issue we will follow four strategies proposed by I.R. White et al (2011):

1. Attempt to follow up all randomized participants, even if they withdraw from allocated treatment.
2. Perform a main analysis of all observed data that are valid under a plausible assumption about missing data.
3. Perform sensitivity analyses to explore the effect of departures from the assumptions made in the main analysis.
4. Account for all ITT study population participants, at least in the sensitivity analyses.

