5.3. Prohibited Medications and Restrictions

- Allopurinol and other urate lowering agents (e.g., probenecid, rasburicase) for the treatment of gout. Patients treated with uric acid lowering agents for elevated uric acid levels with no history of gout can, with the agreement of their treating physician, undergo a 2 month washout of uric acid lowering medication and then be tested to determine if uric acid entry criteria are met.
- Herbal supplements that may have urate lowering actions (e.g., Devil's Claw or Harpagophytum procumbens, Indigenous cinnamon or Cinnamomum osmophloeum, Skunkvine or Paederia scandens or Paederia foetida)
- Azathioprine
- 6-Mercaptopurine
- Didanosine
- Warfarin
- Tamoxifen
- Amoxicillin/ampicillin
- Any other drug for which there is evidence of interaction with allopurinol
- Dual RASB therapy (i.e., another RASB medication in addition to that already in use)
- Non-RASB antihypertensives that are not listed in the PERL approved menu of antihypertensive drugs, unless these were in use before joining the study.

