11.1. Analysis Population

For most of the analyses, including the primary efficacy analysis described in section 11.3, an intention to treat (ITT) analytical approach will be employed. Accordingly, the population for statistical analysis will consist of all randomized study participants considered in their original randomization group, regardless of treatment discontinuation or loss to follow-up.

Selected secondary efficacy analyses will be performed using a per-protocol analytical approach. In this case, the analysis population will consist of the ITT population excluding data points which 1. had cumulative exposure to the study medication from randomization that was less than 80% of the theoretical full exposure; or 2. during major protocol deviations (e.g., treatment with prohibited medications), which could affect primary outcome.

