6.7.2. iGFR time trajectory estimated from repeated iGFR measurements	19
6.7.3. eGFR at 4 months after randomization (Visit 7).....	20
6.7.4. eGFR time trajectory	20
6.7.5. Time to serum creatinine doubling or ESRD	21
6.7.6. Urinary AER at the end of the wash-out period.....	21
6.7.7. Urinary AER during the last three months of the treatment period (Visits 15 and 16).	22
6.7.8. Time to fatal or non-fatal cardiovascular events	22
6.8. Other analyses	23
6.8.1. Subgroup analyses.....	23
6.8.2. Analyses of safety outcomes	24
6.8.3 Analyses of other measures	24
6.8.4. Analysis of the effect of post-randomization sUA changes on iGFR value at Visit 17	25
6.8.5. Time to 40% eGFR decrease.....	26
6.8.6. Time to doubling of serum creatinine, end-stage renal disease (ESRD), or cardiovascular/renal death.....	26
6.9. Model assumptions and alternative analyses	27
ACKNOWLEDGEMENTS.....	28
REFERENCES	29
APPENDIX I. Study Objective, Study Design, Outcomes & Statistical Analysis and Data Management Sections from Protocol.....	30

1. Overview

DESIGN:

- Multicenter, double-blind, placebo-controlled, parallel-group randomized clinical trial.
- N=530 total number of subjects

STUDY POPULATION:

- Type 1 Diabetes
- Inclusion/Exclusion Criteria listed in the Study Protocol

STUDY TREATMENTS:

- Oral allopurinol or placebo administered for 3 years followed by a 2-month drug washout

PRIMARY OUTCOME MEASURE:

[figure not shown]
- iGFR at the end of the 2-month wash-out period following the 3-year intervention

STATISTICAL ANALYSIS PLAN:

- This plan will be finalized prior to the database lock and unblinding of treatment groups

2. Schema

Figure 2.1. PERL Study Schema

3. Rationale for Adjustments of Statistical Analysis Plan as Compared to Protocol (Version 10, approved by DSMB on March 6, 2018)

Changes from the protocol-specified definitions of aims, outcomes, and statistical analytical approaches are outlined below. These changes reflect internal discussions since the initiation of the study that have not been incorporated as protocol amendments, but were discussed during the preparation of the Statistical Analysis Plan. These changes and the rationale for their implementation are documented herein and represent changes made prior to the database lock and unblinding of the study.

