3.8. Modifying definition of per-protocol analysis set

RATIONALE:

Following internal discussion we modified the per-protocol definition as follows.

PROTOCOL:

- **Per Protocol:** ... The per protocol population will exclude subjects ... as well as data points for which the cumulative exposure to the study medication from

randomization to that time point was less than 80% of the theoretical full exposure (see Section 11.1 in the protocol).

SAP:

- **Per Protocol:** ... The per protocol population will exclude subjects ... for whom the average drug exposure was less than 80% (see Section 11.1 in the protocol).

4. Study Aim

The study aim is to determine whether lowering serum UA by means of oral allopurinol is effective in preventing or slowing decline of renal function in T1D patients with history and/or presence of microalbuminuria or moderate macroalbuminuria, or with ongoing GFR loss regardless of history or presence of albuminuria, who have only mildly or moderately impaired kidney function.

5. Study Estimands

This section describes the primary and secondary estimands for corresponding endpoints and variables of interest. We follow ICH-E9 (R1) recommendations and specify estimands in terms of four attributes defining the treatment effect of interest:

- A1. The target population
- A2. The variable (or endpoint) to be obtained for each patient that is required to address scientific question of interest
- A3. Strategies for addressing intercurrent events
- A4. The population summary for the variable (endpoint), that provides a basis for a comparison between treatment conditions.

In Table 5.1. we include various intercurrent events that occurred in the PERL study and divide them into three groups, based on their implications for subsequent data collection of the endpoint of interest.

Table 5.1. Groups of intercurrent (IC) events in PERL study

Group of IC events	IC event	Implications for Post-IC data
Group A	Non-adherence to study drug schedule	Post-IC data are collected, but their interpretation may be affected depending on the estimand of interest
	Permanent discontinuation of study drug	
	Use of prohibited medication	
	Missed scheduled visit	
Group B	ESRD treatment (hemodialysis or transplant for ESRD subjects)	Post-IC data do not contain any relevant information about estimands of interest and for this reason they are not collected
Group C	Early discontinuation from the study	Post-IC data cannot be collected
	Terminal event, i.e. death	

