6.1. Study populations

Two study populations will be defined for the purpose of data analysis:

- **Modified Intention to Treat (mITT):** The mITT analysis set consists of all subjects enrolled in PERL, randomized to study medication, and receiving at least one dose of study medication.
- **Per Protocol:** The per protocol analysis set will consist of a subset of mITT subjects. The per protocol population will exclude subjects with major protocol deviations (defined as receiving the wrong study medication) as well as data points for which the cumulative exposure to the study medication from randomization to that time point was less than 80% of the theoretical full exposure (see Section 11.1 in the protocol).

To account for missing values in any specific analysis, all subjects meeting the study population definitions will be included in the analysis using (1) appropriate analytical approaches that allow for missing values under plausible missing data mechanisms, or (2) analytical methods (defined within specific analyses) that allows the imputation of missing outcomes.

Since the mITT approach can result in the need to analyze data with missing values of the outcomes (or covariates), we will follow four strategies proposed by I.R. White et al (2011):

1. Attempt to follow up all randomized participants, even if they withdraw from allocated treatment.
2. Perform a main analysis of all observed data that are valid under a plausible assumption about missing data.
3. Perform sensitivity analyses to explore the effect of departures from the assumptions made in the main analysis.
4. Account for all mITT study population participants, at least in the sensitivity analyses.

Note that this approach is tailored to mITT population and deviates slightly from the “all randomized participants” suggested by White.

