Visit 12	N_Visit 12/N (xx%)	N_Visit 12/N (xx%)	N_Visit 12/N (xx%)
Visit 13	N_Visit 13/N* (xx%)	N_Visit 13/N* (xx%)	N_Visit 13/N* (xx%)
Visit 14	N_Visit 14/N* (xx%)	N_Visit 14/N* (xx%)	N_Visit 14/N* (xx%)
Visit 15	N_Visit 15/N* (xx%)	N_Visit 15/N* (xx%)	N_Visit 15/N* (xx%)
Visit 16	N_Visit 16/N* (xx%)	N_Visit 16/N* (xx%)	N_Visit 16/N* (xx%)
Visit 17	N_Visit 17/N* (xx%)	N_Visit 17/N* (xx%)	N_Visit 17/N* (xx%)
Completed Across All Visits	ΣN_i	ΣN_i	ΣN_i
% Completed of Total	$\Sigma N_i / n = xx\%$	$\Sigma N_i / n = xx\%$	$\Sigma N_i / n = xx\%$
Analysis Sets for Primary Endpoint:			
mITT Analysis Set ¹	N	N	n
Per Protocol Analysis Set ²	N	N	n

¹ modified intention to treat (mITT) analysis set will consist of all subjects enrolled in PERL, randomized to study medication who received *at least one dose* of study medication.

² per-protocol analysis set will consist of a subset of mITT subjects. The per-protocol analysis set will exclude data points which 1. had cumulative exposure to the study medication from randomization less than 80% of the theoretical full exposure; or 2. with major protocol deviations (e.g., treatment with prohibited medications).

Note: N* = number assessable at this point, i.e., denominator reflects loss from WD, LFU & deaths;

Table 7.3. Demographics and Baseline Characteristics by Treatment Group. ITT Analysis Set.

Variable Statistic or Category	Treatment Group	
	Allopurinol N=	Placebo N=
Age (years)		
Mean (SD)	xx.x (xx.xx)	xx.x (xx.xx)
Median (Q1, Q3)	xx.x (xx.x, xx.x)	xx.x (xx.x, xx.x)
Min, Max	xx, xx	xx, xx
N missing	x	x
BMI (kg/m²) (Visit 4)		
Mean (SD)	xx.x (xx.xx)	xx.x (xx.xx)
Median (Q1, Q3)	xx.x (xx.x, xx.x)	xx.x (xx.x, xx.x)
Min, Max	xx, xx	xx, xx
N missing	x	x
Diabetes duration (years)		
Mean (SD)	xx.x (xx.xx)	xx.x (xx.xx)
Median (Q1, Q3)	xx.x (xx.x, xx.x)	xx.x (xx.x, xx.x)
Min, Max	xx, xx	xx, xx
N missing	x	x
SBP (mm Hg) (Visit 4)		
Mean (SD)	xx.x (xx.xx)	xx.x (xx.xx)
Median (Q1, Q3)	xx.x (xx.x, xx.x)	xx.x (xx.x, xx.x)
Min, Max	xx, xx	xx, xx
N missing	x	x
DBP (mm Hg) (Visit 4)		
Mean (SD)	xx.x (xx.xx)	xx.x (xx.xx)
Median (Q1, Q3)	xx.x (xx.x, xx.x)	xx.x (xx.x, xx.x)
Min, Max	xx, xx	xx, xx
N missing	x	x
BP (Visit 4), n (%)		
SBP > 140 or DBP > 90 mm Hg	xx (xx%)	xx (xx%)

SBP \leq 140 and DBP \leq 90 mm Hg	xx (xx%)	xx (xx%)
Missing	xx (xx%)	xx (xx%)
On RASB at Visit 2	xx (xx%)	xx (xx%)

Table 7.3. Demographics and Baseline Characteristics by Treatment Group. ITT Analysis Set. (continued)

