15	0	.85	.90
9	6	.83	.89
12	6	.82	.88
15	6	.80	.87

Summary of Changes to the Statistical Analysis Plan

The first statistical analysis plan for the PERL status (version dated February 22, 2017) was prepared for inclusion as an appendix to the NIH application for renewal of the grant supporting this clinical trial. This SAP was approved by the Steering Committee but was not reviewed by NIDDK or the PERL DSMB.

A subsequent SAP version (dated May 14, 2019) was prepared as the trial was approaching completion. This was reviewed and approved by the Steering Committee, NIDDK, and the DSMB. The main changes in this version as compared to the previous one (dated February 22, 2017) were):

- Section 3. Rationale for adjustments of the SAP as compared to Protocol
 - Addition and justification of several adjustments to the analyses detailed in the Protocol (v10, dated March 6, 2018).
- Section 5. Study estimands
 - Re-framing of data analysis in terms of “Study estimands”, in order to follow ICH-E9 (R1) recommendations.
- Section 6. Analytical strategy:
 - 6.1. Study population.
 - Revision of the definition of the ITT and per protocol populations.
 - Addition of details regarding the imputation methods.
 - 6.3. Visit Windows.
 - Specification of wider windows for V11, V16, and V17 to ensure that all iGFR are analyzed.
 - Addition of procedure to avoid temporal overlap of iGFR and non-iGFR visits.
 - Creation of separate tables for non-iGFR and iGFR visit windows (Tables 6.3.1 and 6.3.2).
 - Addition of “Time since randomization attributed to visit window” to tables with visit windows.
 - Section 6.4. Baseline Covariates
 - Addition of methods to impute missing values for baseline covariates.
 - Section 6.5 (New) Missing values
 - Description of methods to account for missing values.
 - Section 6.6. Analysis of the primary estimand
 - Miscellaneous changes to make the analysis consistent with the re-framing in terms of Study estimands and for the more detail description of imputation methods.
 - Addition of the tipping point sensitivity analysis to check the robustness of the MAR assumption.
 - Section 6.7. Analysis of secondary estimands
 - Miscellaneous changes to make analysis consistent with the re-framing in terms of Study estimands and for the more detail description of imputation methods.
 - Section 6.8. Other analyses
 - Section 6.8.1 changes in cut-offs for stratified analyses to make them consistent with changes made in Section 3.

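### The SAP's per-protocol set drops the protocol's prohibited-medication criterion without listing the change, so the secondary per-protocol analysis keeps iGFR values the protocol would remove

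*SAP*

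**What the plan says.** Protocol 11.1 builds the per-protocol analysis by removing data points from the ITT population on two grounds. One is cumulative exposure below 80% of the theoretical full amount. The other covers data points "during major protocol deviations (e.g., treatment with prohibited medications), which could affect primary outcome". Protocol 5.3 gives the prohibited list, which includes urate-lowering agents and "Dual RASB therapy (i.e., another RASB medication in addition to that already in use").

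SAP 6.1 refers to protocol 11.1 but sets a different rule. It excludes whole participants, either for "major protocol deviations (defined as receiving the wrong study medication") or for average drug exposure below 80%. Prohibited medication is not mentioned.

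SAP Section 3 opens by stating: "Changes from the protocol-specified definitions of aims, outcomes, and statistical analytical approaches are outlined below". Section 3.8 then deals with this very definition and gives the new rule as "The per protocol population will exclude subjects ... for whom the average drug exposure was less than 80" per cent. Both the protocol side and the SAP side of that comparison have an ellipsis where the deviation criterion belongs.

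The per-protocol set is used once for efficacy, in SAP 6.6.2 item 2, which repeats the primary analysis of iGFR at Visit 17 on that set.

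**The concern.** A per-protocol analysis is meant to show the treatment contrast among people treated as planned. The protocol's criterion addressed off-plan drugs that could affect the endpoint, with prohibited medication as its only named example. The SAP's definition covers a dispensing error and nothing else.

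This is not a purely theoretical gap. SAP Section 5 introduces Table 5.1 as listing intercurrent events that occurred in the trial, and use of prohibited medication is one of them. The same table warns that interpretation of later data may be affected, depending on the estimand. The primary estimand ignores these events on purpose. The per-protocol analysis was the place where the protocol dealt with them, and under SAP 6.1 it no longer does so. A reader who compares the per-protocol and ITT results would assume that such values had been removed.

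**Working it through.** No sample-size, power or alpha figure is at issue. The check compares texts and then asks how far the remaining exposure rule covers the gap.

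**Step 1: the texts side by side.**

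| Source | Deviation criterion | Unit excluded |
|---|---|---|
| Protocol 11.1 | Major deviations that could affect the primary outcome; example given is prohibited medication | Data points |
| SAP dated February 2017, 6.1 | "major protocol deviations (defined as receiving the wrong study medication) as well as data points" (exposure rule follows) | Participants for deviations, data points for exposure |
| SAP dated February 2017, Table 7.2 footnote | "with major protocol deviations (e.g., treatment with prohibited medications") | Data points |
| Current SAP 6.1 | Wrong study medication only | Participants |

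The February 2017 SAP therefore contradicted itself, and its own Section 3 (items 3.1 and 3.2) did not list the narrowing. In the current SAP, the text that 3.8 presents as the protocol's is not the wording of protocol 11.1; it matches 6.1 of the February 2017 SAP. The Summary of Changes to the SAP has only a general entry: "Revision of the definition of the ITT and per protocol populations". No rationale for dropping the prohibited-medication criterion appears in either place.

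**Step 2: what the 80% rule still catches.** Protocol 5.5.1 stops study drug when a participant needs allopurinol or a drug that makes allopurinol contraindicated. Early or sustained use therefore lowers exposure and may take the participant below 80%.

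**Step 3: what it misses.** SAP 6.1 does not define average exposure. I assume the 156-week dosing period used for exposure in SAP 6.8.3.

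- *Late open-label allopurinol.* With full adherence up to the stop, the 80% threshold is reached at 0.80 × 156 = 124.8 weeks. Equivalently, 0.20 × 156 = 31.2 weeks of study drug can be missed. With 90% adherence (an illustrative value) the stop must come later: (0.80 / 0.90) × 156 = 138.7 weeks. A placebo participant who switches after that point and is still on allopurinol at Visit 16 (week 156) or Visit 17 (week 164) stays in the set.
- *Dual RAS blockade.* It is prohibited in protocol 5.3 but is not among the reasons in 5.5.1 for stopping study drug, so exposure can remain at 100%.
- *Washout use.* Weeks 156 to 164 lie outside the dosing period, so a prohibited drug taken then cannot change exposure. The primary endpoint is measured at week 164.

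**Step 4: the unit affected.** The model uses three post-baseline iGFR values per participant (Visits 11, 16 and 17). The protocol rule removes a value only if it was obtained during the deviation. A short course that falls between iGFR visits removes nothing.

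**The case against.** The case on the other side has real weight.

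- *Scope.* This is one supportive analysis. Someone might infer that the primary result is compromised. It is not: under the primary estimand, prohibited medication is ignored by design, consistent with ITT.
- *Disclosure.* The ellipses in 3.8 might be read as concealment. The documents do not support that. The narrow definition is stated openly in 6.1, protocol 11.1 is reproduced in the SAP appendix, and the May 2019 version was approved by the Steering Committee, NIDDK and the DSMB. What stands is that Section 3 claims to outline the changes and omits this one.
- *Latitude.* Protocol 11.1 gives prohibited medication only as an example, and Section 11 leaves detail to the SAP. The SAP may refine the definition, but dropping the sole named example is a change that needs listing and a reason.
- *Mechanism.* It is tempting to say that every prohibited drug alters GFR. Much of the list in protocol 5.3 is there because of interaction with allopurinol. The clearer cases are urate-lowering agents, which carry the trial's own hypothesis and a possible haemodynamic effect (protocol 7.1), and dual RAS blockade. For RAS blockers the documents support only a listed risk of increased serum creatinine (protocol 13.4.3), not a measured effect on iGFR.
- *Size.* One might assume that 1–3% of 530 are affected and count 5–16 participants wrongly kept. The rate is not in the documents, and participants are the wrong unit because the protocol drops data points.
- *Week 125.* It is not true that anyone stopping after week 125 is retained; this needs full adherence beforehand.

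**Conclusion.** The point stands at a modest level. SAP 6.1 is narrower than the protocol section it cites, and neither 3.8 nor the Summary of Changes says so. The exposure rule covers part of the gap but leaves the three routes above open.

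The consequence is confined to SAP 6.6.2 item 2, which would keep some iGFR values that the protocol removes. Placebo values taken on allopurinol pull the arms together if allopurinol has an effect. Values taken on dual RAS blockade have no predictable direction and mainly add noise.

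The number of such values cannot be derived from the documents; it may be small, because only three scheduled measurements per participant count. The conclusion rests on the text comparison and does not depend on any assumed frequency. The week-125 figure rests on full prior adherence and on reading average exposure over 156 weeks.

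**What to change.** In SAP 6.1, restore the protocol criterion: exclude iGFR values obtained during prohibited medication that could affect the primary outcome, naming at least urate-lowering agents and dual RAS blockade. Keep the existing exclusions for wrong study medication and exposure below 80%. The test should remain a possible effect on the primary outcome; a separate test based on uric acid would go beyond the protocol.

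Two details need stating. First, this criterion works by data point, while the other two work by participant. Second, the SAP should say whether values excluded in this way are then multiply imputed under 6.5 or left missing.

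In SAP 3.8, replace the text attributed to the protocol with the actual wording of protocol 11.1, so that every remaining difference is visible, including the move from data points to participants for exposure. If the sponsor prefers the narrow definition, 3.8 should list it and justify it.

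The cost is low. Concomitant medications are already recorded at nearly every visit, so no new data are needed, though classifying the drugs should be done blinded. The analysis loses slightly more iGFR values. Exclusion is also on a post-randomisation event that may fall unevenly: protocol 13.5 starts open-label allopurinol when uric acid exceeds 12 mg/dl, which is more likely on placebo. That weakness is common to per-protocol analyses and should be acknowledged when the result is reported.
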